### **11.3.2 Reporting**

To ensure subject safety, every SAE, regardless of suspected causality, occurring after the subject has provided informed consent and until at least 30 days after the subject has stopped study treatment must be reported to the Sponsor-Investigator or designee within 24 hours of learning of its occurrence. Any SAEs experienced after this at least 30 day period should only be reported to the Sponsor-Investigator or designee if the investigator suspects a causal relationship to the study drug. Recurrent episodes, complications, or progression of the initial SAE must be reported as follow-up to the original episode within 24 hours of the investigator receiving the follow-up information. An SAE occurring at a different time interval or otherwise considered completely unrelated to a previously reported one should be reported separately as a new event. Serious adverse event collection begins after the subject has signed informed consent and has received study drug. If a subject experiences a SAE after signing informed consent, but prior to receiving ruxolitinib, the event will NOT be collected unless the investigator feels the event may have been caused by a protocol procedure. Previously planned (prior to signing the informed consent document) surgeries should not be reported as SAEs unless the underlying medical condition has worsened during the course of the study.

Information about all SAEs is collected and recorded on the Serious Adverse Event Report Form. The investigator must assess and record the relationship of each SAE to the

study drug, complete the SAE Report Form in English, and send the completed, signed form by fax within 24 hours to the Sponsor-Investigator via a Sponsor-approved method. The investigator must assess if there is a Reasonable possibility that SAE is related to the study treatment: (no, yes)

All serious adverse events regardless of severity or relationship must be reported to the sponsor-investigator within 24 hours of the investigational staff's knowledge. Please send a completed SAE form to:

UNMC, ATTN: [name]		Sentryx
[contact]	AND	[contact]
[contact]		Helpdesk: [name]

The Sponsor-Investigator will follow UNMC IRB and DSMC safety reporting requirements. Participating sites must follow their local IRB and safety reporting requirements.

The original copy of the SAE Report Form and the fax confirmation sheet must be kept with the case report form documentation at the study site.

Follow-up information is sent to the same person to whom the original SAE Report Form was sent, using a new SAE Report Form stating that this is a follow-up to the previously reported SAE and giving the date of the original report. Each re-occurrence, complication, or progression of the original event should be reported as a follow-up to that event regardless of when it occurs. The follow-up information should describe whether the event has resolved or continues, if and how it was treated and whether the subject continued or withdrew from study participation.

If the SAE is not previously documented in the Investigator's Brochure for study medication (new occurrence) and is thought to be related to the study drug, a Sponsor's associate may urgently require further information from the investigator for Health Authority reporting.

The Sponsor-Investigator may need to issue an Investigator Notification (IN), to inform all investigators involved in any study with the same drug that this SAE has been reported. Suspected Unexpected Serious Adverse Reactions (SUSARs) will be collected and reported to the competent authorities and relevant ethics committees in accordance with regulatory requirements.

#### **11.4      Pregnancies**

Pregnancy, in and of itself, is not regarded as an adverse event, unless there is suspicion that study medication may have interfered with the effectiveness of a contraceptive medication or method. The procedures that will be followed based on whether a pregnancy is confirmed by a positive serum test result are listed below:

- Investigator and subject must notify each other immediately
- Investigator must notify the Sponsor immediately
- Discontinue study medication immediately
- Perform the required End-of-treatment visit study evaluations
- Investigator must complete and submit the Pregnancy Initial and Follow-up report forms to the Sponsor

**To ensure subject safety, each pregnancy in a subject during maternal or paternal exposures to study drug must be reported within 24 hours of learning of its occurrence.** Data on fetal outcome and breast-feeding are collected for regulatory reporting and drug safety evaluation. The pregnancy should be followed up to determine outcome, including spontaneous or voluntary termination, details of the birth, and the presence or absence of any birth defects, congenital abnormalities, or maternal and/or newborn complications by following until the first well-baby visit. Pregnancy should be recorded on a Clinical Study Pregnancy Form and reported by the investigator to the Sponsor-Investigator. Pregnancy follow-up should be recorded on the same form and should include an assessment of the possible relationship to the study drug of any pregnancy outcome and follow-up to the first well-baby visit. **Any SAE experienced**

**during pregnancy must be reported on the SAE Report Form and needs to be reported to the Sponsor.**

## **11.5      Warnings and Precautions**

No evidence available at the time of the approval of this study protocol indicated that special warnings or precautions were appropriate, other than those noted in the provided Investigator Brochure. Additional safety information collected between IB updates will be communicated in the form of Investigator Notifications. This information will be included in the subject informed consent and should be discussed with the subject during the study as needed.

# **12.0    STATISTICS**

## **12.1       Study Populations**

The populations to be analyzed include the following:

Intent-to-treat (ITT) population - Subjects enrolled in the study.

Evaluable population – Subjects who had completed 2 cycles of therapy with response assessments or progressed before the evaluation of the primary endpoint.

Safety evaluable population. - Subjects who received at least one dose of study medication.

## **12.2       Efficacy Analysis**

Primary efficacy analyses will be based on both the ITT and evaluable populations.

Secondary efficacy analyses will be based on ITT population only.

### **12.2.1       Primary Efficacy Analyses**

Primary endpoint

The primary objective of the study is to evaluate subject overall response rate (ORR) after 6 cycles for each of the subject cohorts. The description provided in this section includes the primary analyses for the primary objective.

Statistical hypothesis and sample size justification

Subjects meeting the stated eligibility requirements will be enrolled onto the study. Subjects will be grouped into cohorts 1) DLBCL ABC 2) DLBCL GCB 3) PTCL and 4) OTHER SUBTYPES (subjects who are not able to be placed into cohorts 1, 2, and 3), based upon a central determination of immunohistochemistry and gene-expression profile. A target sample size of 30 is planned for cohorts 1, 2, and 3. Cohorts 1, 2, and 3 will have a minimum of 10 and a maximum of 30 subjects. There is no minimum or maximum requirement for Cohort 4, since there is a very low number of subjects anticipated for this cohort. (Maximum in all cohorts is 90 subjects).

These sample sizes are based on a 3-stage design of alpha=0.07 with power of 77% ( $\beta=0.23$ ) to test the null hypothesis that ORR after 6 cycles will be  $\leq 10\%$  (not considered clinically compelling) versus the alternative hypothesis that ORR will be  $\geq 25\%$  (considered clinically meaningful in this patient population) within each cohort. Based on the simulation study, to maintain the above type I and II errors, two interim analyses for futility will be performed for each cohort separately according to the following stopping rule:

- 1) The first interim analysis will occur when 10 subjects have been enrolled in the cohort. If there are any responders (CR+PR) observed among the 10 subjects, enrollment will continue; otherwise, enrollment will be suspended and these 10 subjects will be followed to further assess their responses. During this follow-up period, as soon as one response is observed, enrollment will resume. If no response is observed after the 10 subjects have been fully assessed after 6 cycles, the trial will be terminated for futility.

- 2) The second interim analysis will occur when 20 subjects have been enrolled in the cohort. If there are 3 or more responders (CR+PR) observed among the 20 subjects, enrollment will continue; otherwise, enrollment will be suspended and these 20 subjects will be followed to further assess their responses. During this follow-up, as soon as 3 or more responders are observed, enrollment will resume. If there are < 3 responders observed after the 20 subjects have been fully assessed, the trial will be terminated for futility.
- 3) At the end of the trial, if there are  $\geq 6$  responders (CR+PR) observed among the 30 subjects, the null hypothesis will be rejected and the drug is valuable to pursue further research; otherwise we fail to reject the null hypothesis and futility of the drug will be claimed.

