### **9.2.2 Dose Increases**

The initial dose of ruxolitinib will be determined by the Baseline platelet count value. After every 2 cycles (post cycle 2, 4, 6, etc.) of therapy, at the discretion of the

investigator, the dose may be increased in 5 mg BID increments, to a maximum dose of 25 mg BID for subjects who meet all three of the following conditions:

1. Inadequate efficacy is demonstrated by no response or stable disease relative to baseline.
2. Platelet count is  $\geq 50,000/\mu\text{L}$  and platelet count has never been below  $50,000/\mu\text{L}$  at a prior laboratory evaluation since Baseline.
3. Absolute neutrophil count levels have remained at or above  $1000/\mu\text{L}$  since baseline.
4. No grade 4 anemia has been observed since baseline.

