**Table 3 Optional Dose Increase or Mandatory Reduction Levels for Subjects initiating treatment at 10 mg daily**

+3 Dose Level	25 mg BID daily for 28 days per cycle
+2 Dose Level	20 mg BID daily for 28 days per cycle
+1 Dose Level	15 mg BID daily for 28 days per cycle
Starting Dose	10 mg BID daily for 28 days per cycle
-1 Dose Level	5 mg BID daily for 28 days per cycle

In summary, it is the intention to identify the optimal dose for each individual subject over the first several weeks of therapy as follows:

- Starting dose determined by baseline platelet count level.
- Optional dose increase after every 2 cycles if an objective response (PR or CR) was not achieved and no significant thrombocytopenia or neutropenia was observed.
- Frequent monitoring of hematology parameters, with mandatory dose decreases for toxicities.

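### Could first responses after cycle 6 count towards the final 6-of-30 rule, although the null hypothesis is about response after 6 cycles?

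*Combined protocol and SAP*

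**What the plan says.** Section 12.2.1 opens by defining the primary objective as the overall response rate after 6 cycles in each cohort. It then gives the design: three stages, alpha 0.07, power 77%, "to test the null hypothesis that ORR after 6 cycles will be" at most 10%, against an alternative of at least 25%. Three rules follow.

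- **First interim, 10 subjects.** At least one responder is needed to go on. The stopping condition names the window: "If no response is observed after the 10 subjects have been fully assessed after 6 cycles".
- **Second interim, 20 subjects.** At least 3 responders are needed. The stopping condition refers to fewer than 3 "responders observed after the 20 subjects have been fully assessed", with no cycle number.
- **Final, 30 subjects.** The rule begins "At the end of the trial, if there are" and requires at least 6 "responders (CR+PR) observed among the 30 subjects, the null hypothesis will be rejected". It gives no cycle number.

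Elsewhere, sections 4.1 and 5.1 state the objective and endpoint without a time point. Section 7.4 lets subjects who are benefiting stay on treatment until progression, toxicity or another listed reason. Section 7.3 and footnote c of section 7.1 continue restaging every 2 cycles, and use the post-cycle-6 assessment as the point after which responders may be scanned less often. Section 9.2.2 allows optional dose increases "After every 2 cycles (post cycle 2, 4, 6, etc.) of therapy" where "Inadequate efficacy is demonstrated by no response or stable disease relative to baseline", subject to blood-count conditions.

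**The concern.** The 6-cycle limit is written into the endpoint, the hypothesis and the first interim, but not into the second interim or the only rule that can reject the null. Taken literally, a count of responders at the end of the trial has no upper time limit.

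The protocol leaves room for late first responses. Stable disease is not a reason to stop, restaging continues past cycle 6, and dose increases remain possible then. Under Table 3, a subject starting at 10 mg BID needs three 5 mg steps to reach the top level. If these are taken after cycles 2, 4 and 6, that level starts on day 6 × 28 + 1 = 169, just outside the window.

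If late responses were counted, the test would compare a larger quantity with a 10% null set for a 6-cycle rate. The false-positive rate would exceed the plan's figure. Early enrollees would have longer to become responders than late ones. The outcome turns on one subject, 5 against 6 of 30, so a single late response could reverse a cohort's conclusion.

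**Working it through.** **Inputs (section 12.2.1).** Stages of 10, 20 and 30 subjects; continue at 1 or more of 10 and 3 or more of 20; reject at 6 or more of 30; null 10%, alternative 25%; stated alpha 0.07 and power 77%.

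**Step 1: reproduce the plan's figures.** Let A, B and C be the responders in successive groups of 10, independent Binomial(10, p). Then

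P(reject) = Σ P(A=a) P(B=b) P(C=c) over a ≥ 1, a+b ≥ 3, a+b+c ≥ 6.

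- p = 0.10: 0.0663. The plan says 0.07.
- p = 0.25: 0.7636. The plan says 77%, from simulation.

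With one response probability at all three looks, the cut-offs deliver the stated error rates.

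**Step 2: add late first responses at the final look only.** Each subject first responds by cycle 6 with probability p = 0.10, after cycle 6 with probability q, or never. Both interims use 6-cycle responses. Given e responders by cycle 6, the late responders among the other 30 − e are Binomial(30 − e, q/(1 − p)), and the null is rejected if e plus that number is at least 6. The documents give no q, so a range is shown.

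| Assumed q | P(reject) at a 6-cycle rate of 10% | Late share of all responders, q/(0.10 + q) |
|---|---|---|
| 0 | 0.066 | 0 |
| 0.1% | 0.068 | 1% |
| 0.25% | 0.072 | 2% |
| 0.5% | 0.077 | 5% |
| 1% | 0.088 | 9% |
| 2% | 0.112 | 17% |
| 3% | 0.134 | 23% |
| 5% | 0.177 | 33% |

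If the second interim also counted late responses, the values at q = 1, 2, 3 and 5% would be 0.093, 0.124, 0.159 and 0.235.

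**Step 3: how often one late response would decide.** The chance of passing both interims and finishing with exactly 5 of 30 by cycle 6 is 7.7%, 14.0%, 13.0% or 7.9% at a true 6-cycle rate of 10, 15, 20 or 25%. That is only the chance of being one short of the cut-off. A reversal also needs a late responder among the other 25. At the null with q = 1%, the chance of at least one is 1 − (1 − 0.01/0.90)^25 = 0.244, so the joint probability is 0.077 × 0.244 = 0.019.

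**Step 4: which reading the text supports.** The section states one null, on response after 6 cycles, and the final rule says that this null is rejected. The first interim defines full assessment as assessment after 6 cycles, and the second uses the same expression without repeating the number. The evaluable population in section 12.1 refers to progression before the primary endpoint is evaluated, which implies a set evaluation point. The post-cycle-6 assessment is a scheduled landmark in sections 7.1 and 7.3. No passage says that later responses enter the count.

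**The case for a change.** The best case for a change is that the plan never says outright that the final count is limited to 6 cycles. Because the first interim spells the limit out, its absence from the other two rules can look deliberate. The repair would take a few sentences and no new data. A choice of window is also better made before a cohort stands at 5 of 30 with one late responder.

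What stands is that the wording is incomplete, and that under the looser reading the direction of the error is certain. Its size is not. At q = 0.1% the false-positive rate is still below 0.07, and the larger figures need a substantial share of all responders to appear for the first time after 6 × 28 = 168 days. Section 7.4 ends treatment at progression, so such a subject must first have gone about 24 weeks without either progressing or responding.

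The dose argument is narrower than it looks. It concerns subjects starting at 10 mg BID, who under section 9.2.1 have baseline platelets of 75,000 to below 100,000/µL, and who take every optional step while meeting the blood-count conditions. Subjects starting at 15 mg BID need two steps and can reach the top level on day 4 × 28 + 1 = 113, inside the window.

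Unequal follow-up is not a separate problem, because it affects the count only if late responses are admitted. The silence of sections 4.1 and 5.1 is not a contradiction either: they are headline statements, and section 12.2.1 supplies the time point.

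**Conclusion.** No change to the plan follows. Section 12.2.1 fixes the window when it defines the endpoint and the null, and the final rule tests that null. The reference to the end of the trial most naturally dates the decision. Applied at all three looks, the 6-cycle window gives alpha 0.066 and power 0.764, in line with the stated 0.07 and 77%.

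The inflation, from 0.068 at 0.1% late first responders to 0.177 at 5% when they enter at the final look only, arises only if an analyst sets aside the section's own endpoint definition. It also depends on a rate that the documents do not give. Repeating the limit in the second and final rules would be tidier, but it would write down what the section already sets and would alter no cut-off, sample size or error rate. Separate tables of late responses by dose level are a matter of preference.

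This conclusion assumes that responders are counted by first CR or PR up to the post-cycle-6 restaging.

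### Final rule claims futility of the drug at 3, 4 or 5 of 30 because ORR ≤10% is not rejected, without setting the result against the 25% target or giving a confidence interval for ORR

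*Combined protocol and SAP*

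**What the plan says.** Section 12.2.1 sets the same hypotheses for cohorts 1, 2 and 3: ORR after 6 cycles of 10% or less against 25% or more. The plan describes the higher rate as "considered clinically meaningful in this patient population". The stated per-cohort error rates are alpha 0.07 and power 77% (beta 0.23), with looks at 10, 20 and 30 subjects.

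The two interim rules describe an action. At the first look: "If no response is observed after the 10 subjects have been fully assessed after 6 cycles, the trial will be terminated for futility". At the second: "If there are < 3 responders observed after the 20 subjects have been fully assessed, the trial will be terminated for futility".

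The third rule states a conclusion. With 6 or more responders among 30, the null is rejected and the drug is judged worth further research. With fewer: "otherwise we fail to reject the null hypothesis and futility of the drug will be claimed".

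Nothing in 12.2.1 compares the final result with 25%, and no confidence interval is specified for ORR. Section 12.2.2 does give 95% intervals for duration of response, progression-free survival and overall survival.

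**The concern.** The last clause of rule 3 joins two different statements. Failing to reject an ORR of 10% or less means that the data do not show activity above 10%. Claiming futility of the drug is a positive finding that useful activity is absent. To support that, the result would have to be set against the rate the plan calls meaningful, and the rule does not do this.

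ORR by cohort is the primary objective, so this clause fixes the headline result. A lymphoma subtype with an inconclusive result could be reported as a demonstrated failure, with no interval beside it to show what the data still allow.

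**Working it through.** **Inputs (all from 12.2.1).** Three stages of 10 subjects; continue with at least 1/10, then at least 3/20; reject with at least 6/30; null rate 0.10, target rate 0.25.

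**Step 1: the plan's own figures.** With b(x; 10, p) the binomial probability of x responders in a stage, the probability of finishing at k of 30 is the sum of b(x1; 10, p) × b(x2; 10, p) × b(x3; 10, p) over x1 ≥ 1, x1 + x2 ≥ 3 and x1 + x2 + x3 = k. Summing over k ≥ 6 gives:
- p = 0.10: 0.0663, against the stated alpha of 0.07;
- p = 0.25: 0.7636, against the stated power of 77%.

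The design reproduces, apart from about half a point of power.

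**Step 2: which results meet the clause.** A cohort reaches 30 only with at least 3 responders in its first 20. The failing final counts are therefore 3, 4 and 5.

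**Step 3: how often this happens at a true ORR of 25%.**
- Stop at the first look: 0.0563.
- Stop at the second look: 0.0617.
- Finish at 3, 4 or 5 of 30: 0.0067, 0.0327 and 0.0790, together 0.118.

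The three parts add to 0.236, which is 1 − 0.7636.

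**Step 4: what each count says about 25%.**
- The likelihood ratio of 25% to 10% at k of 30 is (0.25/0.10)^k × (0.75/0.90)^(30−k); the stopping rules cancel. At k = 5 it is 97.66 × 0.01048 = 1.02.
- The unadjusted one-sided p against 25% is P(X ≤ k) for a binomial with n = 30 and p = 0.25.
- The stage-adjusted p adds the early stops to the final counts up to k: 0.0563 + 0.0617 + 0.0067 = 0.125 at k = 3; adding 0.0327 gives 0.157 at k = 4; adding 0.0790 gives 0.236 at k = 5.

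| Final count | Exact two-sided 95% CI, looks ignored | One-sided p against 25%, looks ignored | Stage-adjusted p | Stage-adjusted 97.5% upper limit | Likelihood ratio, 25% to 10% |
|---|---|---|---|---|---|
| 3/30 | 2.1% to 26.5% | 0.037 | 0.125 | 34.4% | 0.11 |
| 4/30 | 3.8% to 30.7% | 0.098 | 0.157 | 35.1% | 0.34 |
| 5/30 | 5.6% to 34.7% | 0.203 | 0.236 | 36.9% | 1.02 |

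**Step 5: could any failing result exclude 25%?** The stage-adjusted 97.5% upper limits for the early stops are 30.8% at 0/10, 31.5% at 1/20 and 34.3% at 2/20. With the three in the table, every futility outcome has an upper limit above 25%.

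**The case against.** The strongest reply is that rule 3 is an ordinary go/no-go rule. Success means worth further research, and futility is the other branch of the same sentence, so the word may mean only that the criterion was missed. The risk of missing a drug with a 25% ORR is disclosed as beta 0.23. This stands for the decision: not proceeding at 5/30 is legitimate, and neither the cut-off nor the error rates are at fault. It does not stand for the wording, because the clause sets the claim beside the test result as the cohort's conclusion and the plan offers no interval to qualify it. If shorthand was meant, the text should say so.

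Several stronger readings are tempting, and the documents do not support them:
- *No failing count excludes 25% at any level.* The plan sets no level for ORR. With the looks ignored, 3/30 excludes 25% at one-sided 5% (p = 0.037; exact 90% upper limit 23.9%) and at the design's 7%, and its likelihood ratio is about 9 to 1 in favour of 10%. At 4/30, 25% is excluded only at about one-sided 10% (exact 80% upper limit 24.9%).
- *The conclusion at 5/30 is wrong.* A likelihood ratio of 1.02 is neutral. The claim is unsupported, not shown to be false.
- *The wording causes 23.6% wrong calls per cohort, or 55% for at least one of three* (1 − 0.7636³, if all three cohorts are independent and truly at 25%). These figures are the disclosed beta, and about half of the 23.6% arises at the interim looks. Rewording changes neither.

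**Conclusion.** The point holds as a fault in the stated conclusion, not in the design. The futility claim is unsupported at 5/30 and at 4/30, and borderline at 3/30. The part that belongs to rule 3 is a probability of 11.8% per cohort at a true ORR of 25%, two thirds of it at exactly 5/30 (7.9%); 3/30 contributes only 0.7%.

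This rests on independent binomial responses, looks at exactly 10, 20 and 30 subjects with complete assessment, and a two-sided 95% level. That level is an assumption borrowed from the time-to-event endpoints. The result for 5/30 is not sensitive to it: the exact 80% upper limit is still 28.7%. The half-point difference in power is too small to need a correction.

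**What to change.** Keep the 6/30 cut-off and the go/no-go action. Replace the last clause of rule 3 with:

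*otherwise the null hypothesis is not rejected in that cohort and the pre-set criterion for further study is not met; the ORR will be reported with a two-sided 95% confidence interval that accounts for the three stages, and non-rejection alone will not be reported as showing that the ORR is below 25%.*

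The plan should also name the ordering behind the interval. Stagewise ordering and ordering by the observed rate give the same upper limits at 3, 4 and 5 of 30.

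Do not add a condition that the upper limit must fall below 25% before inactivity is claimed. Step 5 shows that no futility outcome of this design could meet it at this level.

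The cost is one sentence and one adjusted interval per cohort. Sample size, cut-offs and error rates do not change. The downside is that a cohort ending at 3 to 5 of 30 is reported as not having met the criterion, and no longer as proven futile.
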